5.2. General Methods

5.2.1. Analyses for Continuous Data

For continuous variables, the data will be summarized using the number of subjects, mean, median, standard deviation, minimum, maximum in accordance with current Pfizer's data and reporting standards. For summary of PK and PD parameters, geometric mean, geometric coefficient of variation (geocv%) will also be included.

5.2.2. Analyses for Categorical Data

For categorical or ordinal variables, number of subjects, numbers and percentages of subjects meeting the categorical criteria will be supplied in accordance with current Pfizer's data and reporting standards.

5.2.3. Analyses for Count Data

Separate models will be run for each pairwise comparison between the historical control group and each dose cohort. The frequency of bleedings will be analyzed using a negative binomial model. Log transformed duration of time on study will be included as an offset variable in the model.

Sample SAS codes are provided as follows:

```
PROC GENMOND Data=sample;
  Where dose='300mg SC';
  Class trt;
  Model count=trt/dist=negbin link=log offset=logtime alpha=0.2 ;
  Estimate 'PF-06741086 - PCB' trt 1 -1;
  Estimate 'PF-06741086' intercept 1 trt 1/alpha=0.2;
  ods output ParameterEstimates=pvalue estimates=est;
```

Run;

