5.1. Hypotheses and Decision Rules

Prophylactic treatment with PF-06741086 will be considered superior to On Demand treatment with respect to ABR reduction if 1) the upper limit of the 2-sided 80%CI of the ratio of ABR in PF/historical On Demand is <1 and 2) the estimate of the ratio of ABR in PF/historical On Demand ≤ 0.3 . Drug will be considered not superior to On Demand treatment if the lower limit of the 2-sided 80%CI of the ratio of PF/historical On Demand >0.3 .

The primary efficacy endpoint in the four dose cohorts will be tested in a hierarchical order to control the overall family-wise error rate. The efficacy test will first be performed in the dose cohort with the highest PK exposure (eg, C_{trough} and/or AUC) that is proven to be safe and tolerated. If the result is significant, the ABR will be tested against the historical On Demand group in the dose cohort with the next highest PK exposure. The test procedure will continue until the dose cohort with the lowest PK exposure is tested against the historical On Demand group.

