6.2. Secondary Endpoint(s)

6.2.1. Efficacy Endpoint

6.2.1.1. Statistical Analysis

The efficacy analysis will be conducted in the PPAS. A historical On Demand group will be constructed using the following internal Pfizer studies: ReFacto AF 3082B2-4432 (B1831004), BeneFIX B1821010, and BeneFIX 3090A1-400 (B1821004). Subjects who are on On Demand treatment in B1831004, as well as data from the On Demand period in B1821004 and B1821010 will be used to construct the historical On Demand group. The resulting dataset will be further filtered to match the key inclusion/exclusion criteria of B7841002 based on age and factor activity ($18 \leq \text{age} \leq 65$ and factor activity $\leq 1\%$). Outliers with extremely high ABR will be removed from the pooled On Demand group, if appropriate. All resulting subjects will be included in the historical control group.

The frequency of bleedings will be analyzed using a negative binomial model as detailed in Section 5.2.3. The ratio of ABR and its 80% 2-sided CI in the PF-06741086 arm versus that in the historical On Demand group will be generated for each dose cohort. The corresponding p-value will also be presented. Model based ABR and its 80%CI will be generated for each dose cohort.

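### SAP 5.2.3 sample code: the ratio ESTIMATE lacks the 80% level that the decision rule needs, and its direction depends on a treatment coding the SAP does not state

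*SAP*

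**What the plan says.** **Decision rule (SAP 5.1).** Superiority has two conditions: "the upper limit of the 2-sided 80%CI of the ratio of ABR in PF/historical On Demand is <1", and "the estimate of the ratio of ABR in PF/historical On Demand" being at most 0.3. There is also a negative verdict: "Drug will be considered not superior to On Demand treatment if the lower limit of the 2-sided 80%CI" of the same ratio is above 0.3.

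**Analysis text (SAP 6.2.1.1).** "The ratio of ABR and its 80% 2-sided CI in the PF-06741086 arm versus that in the historical On Demand group will be generated". This is done cohort by cohort, and a model-based ABR with its 80% interval is also required for every cohort.

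**Sample code (SAP 5.2.3).**
- The model line carries the 80% level: "Model count=trt/dist=negbin link=log offset=logtime alpha=0.2".
- The ratio line does not: "Estimate 'PF-06741086 - PCB' trt 1 -1".
- The ABR line does: "Estimate 'PF-06741086' intercept 1 trt 1/alpha=0.2".
- The CLASS statement names `trt` with no order or reference option. The values of `trt` are not shown anywhere.
- The WHERE clause keeps only records with the 300 mg SC dose value.
- The parameter table is saved as `pvalue` and the ESTIMATE results as `est`.

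**The concern.** The line that feeds the decision rule is the one without the 80% level. If MODEL already passed its level to the ESTIMATE statements, the `alpha=0.2` on the ABR line would be unnecessary. Its presence suggests that the author did not expect carry-over. In that case one run yields two sets of limits for one contrast: 80% limits in a data set named `pvalue`, and wider limits in the data set where the ratio is actually labelled. A programmer would naturally take the labelled row. A 95% interval reported as 80% is hard to notice.

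The second issue is direction. Coefficients `1 -1` mean first level minus second, and `intercept 1 trt 1` returns the first level. Both labels are right only if PF-06741086 is the first level of `trt`, and the SAP does not say that it is. The comparator label 'PCB' also does not match the comparator in the text, which is the historical On Demand group.

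**Working it through.** **1. The plan's own figure.** Protocol 9.1 gives 6 subjects per cohort, a control rate of 2.36 per patient-month, 3 months, an 85% reduction (ratio 0.15), one-sided alpha 0.1, and power above 80%. One-sided 0.1 corresponds to a two-sided 80% interval. Control-group size is not given, so take 6 controls as the low end.
- Expected control bleeds: 2.36 × 3 × 6 = 42.48. Expected drug bleeds: 0.15 × 42.48 = 6.37.
- Poisson SE of the log ratio: √(1/42.48 + 1/6.37) = 0.425.
- Power: Φ(|ln 0.15|/0.425 − 1.2816) = 99.9%.

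The stated power is reproduced. With negative binomial dispersion k of 0.5 to 1.0 and 6 to 100 controls (both assumed), it is 91% to 99%.

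**2. What the missing level does.** The z-values are 1.2816 (80%) and 1.9600 (95%), so the log-scale interval is 1.9600/1.2816 = 1.53 times as wide.

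'Not superior' needs estimate × exp(−z·SE) > 0.3, that is, an estimate above 0.3 × exp(z·SE):

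| Assumed SE | Threshold, 80% limits | Threshold, 95% limits |
|---|---|---|
| 0.38 | 0.49 | 0.63 |
| 0.43 | 0.52 | 0.70 |
| 0.60 | 0.65 | 0.97 |
| 0.66 | 0.70 | 1.09 |

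The SE is an assumption, because the SAP gives neither dispersion nor control-group size. SE = √(1/μ_control + 1/μ_drug + k/n_control + k/6). At a true ratio of 0.5 with 24 controls, μ_control = 169.92 and μ_drug = 21.24. The SE is then 0.40 for k = 0.5, 0.51 for k = 1 and 0.69 for k = 2.

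**3. How often the negative verdict changes.** By the normal approximation, for true ratio r, the chance that the estimate falls between the two thresholds is Φ(1.9600 − d) − Φ(1.2816 − d), with d = ln(r/0.3)/SE.
- r = 0.5, SE 0.43: d = 1.188, giving 24%.
- r from 0.4 to 0.6, SE from 0.43 to 0.60: 14% to 27%.
- r = 0.15 (the design effect), SE 0.5 to 0.6: 0.3% to 0.7%.

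**4. Superiority.** The estimate must already be at most 0.3. The upper limit can then reach 1 only if SE ≥ −ln(0.3)/z = 1.204/z, which is 0.94 with 80% limits and 0.61 with 95% limits. At SE 0.70 the 95% upper limit is below 1 only for estimates under exp(−1.9600 × 0.70) = 0.25, so estimates from 0.25 to 0.30 would lose superiority. Wider limits cannot turn a failure into a success.

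**5. Direction.** In alphabetical order 'PCB' precedes 'PF-06741086', as do 'Control', 'Historical On Demand' and 'On Demand'. If `trt` held such text values and levels were sorted by value:
- `trt 1 -1` is control minus drug, and a ratio of 0.15 prints as 1/0.15 = 6.7.
- `intercept 1 trt 1` is the control ABR. On the protocol inputs that is 2.36 × 12 = 28.3 under the drug's name, instead of 0.15 × 28.3 = 4.2.

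A negative binomial fit to simulated data (24 controls, 6 treated, true k 0.5) showed the same. Control-first coding gave 6.75 (95% limits 2.53 to 18.0) and an ABR of 27.0 on the line labelled as the drug. The contrast required by the text gave 0.148 (80% limits 0.078 to 0.282) and an ABR of 4.0. The fit was done in Python; SAS was not run. If drug is coded first, for example 1 = drug and 2 = control, both lines are correct as printed.

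**The case against.** The best defence is that this is sample code and the governing prose is clear. SAP 5.1 and 6.2.1.1 both state the 80% level and the direction of the ratio. The procedure name is misspelt, so the block cannot run as printed and someone must retype it. All of this stands: the code is not the only specification of the analysis.

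The MODEL line does carry `alpha=0.2`, and with two treatment levels its `trt` parameter is the same contrast up to sign. Correct 80% limits are therefore available in ParameterEstimates. That also stands, and it limits the level problem to the `est` row. That the ESTIMATE default is 95%, and that levels sort by value, are assumptions about the software which the documents do not state. The repeated `alpha` on the ABR line is consistent with no carry-over but does not prove it.

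Three stronger readings are tempting and not supported:
- *The ratio is reversed.* The group names in the code are free-text ESTIMATE labels, not shown values of `trt`. Reversal is conditional on coding. A ratio near 6.7 would also clash visibly with the descriptive ABRs that SAP 6.2.1.2 requires for the cohorts and the historical group.
- *The WHERE clause silently drops the controls.* Control rows may have been stacked under each cohort's dose value. If they were not, only one treatment level remains and the comparison fails openly.
- *A false superiority claim could follow from the level error.* It could not, because the error only widens the interval.

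**Conclusion.** The point holds as an inconsistency between the sample code and the SAP's own decision rule. The ratio ESTIMATE lacks the 80% level, and the code leaves the direction of the contrast and the identity of the reported ABR to an unstated coding.

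If the `est` limits were used at 95%, the main effect would be to move 'not superior' verdicts to undecided. That matters when the true ratio is around 0.4 to 0.6 (14% to 27% of cohorts at SE 0.43 to 0.60) and hardly at all at the design ratio of 0.15 (under 1%). Superiority is exposed only above an SE of about 0.61, which needs strong overdispersion. These sizes rest on assumed SEs and on the ESTIMATE default being 95%. The direction error is larger if it occurs, but it is conditional and easy to see. The documents do not show that any reported result would be wrong; they show that the code can disagree with the text it implements.

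**What to change.** In SAP 5.2.3:
- Add `/alpha=0.2 exp` to the ratio ESTIMATE, so that the labelled row gives the ratio and its 80% limits directly.
- State the values of `trt` and fix their order or reference, or rewrite the coefficients, so that the contrast is PF-06741086 minus historical On Demand and the ABR line returns the drug cohort.
- Make the WHERE clause keep the cohort plus all historical control rows.
- Replace 'PCB' with the historical On Demand label, and correct the procedure name at the same time.

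LSMEANS with differences and limits at `alpha=0.2` would also work but is optional. The cost is a few lines of sample code. No endpoint, decision rule or data collection changes.

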5.2.4. Mixed Model Repeated Measures (MMRM)

Change from baseline of each PD endpoint will be analyzed using a mixed model for repeated measures (MMRM) with a restricted maximum likelihood method for the estimation of the covariance parameters. The model will include dose, study day and dose by study day interaction as fixed categorical effects as well as baseline value as a fixed effect continuous covariate. Subject will also be included in the model as a random effect. An unstructured covariance matrix will be used to model the within-subject errors. If model fitting issues occur with the unstructured covariance matrix, other covariance structures including Toeplitz, compound symmetry, and autoregressive (1) will be considered. The covariance structure converging to the best fit, as determined by Akaike's information criterion (AIC), will be used as the primary analysis: the competing models will be ranked according to their AIC, with the one having the lowest AIC being the best. The Kenward-Roger approximation will be used to estimate denominator degrees of freedom.

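### The PD repeated-measures model adds a redundant random subject effect to an unstructured covariance, and every named fallback assumes equal variance at all visits

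*SAP*

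**What the plan says.** Protocol 9.4 plans an MMRM fitted by REML for change from baseline in each PD endpoint and leaves the details to the SAP. SAP 5.2.4 supplies them:

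- Fixed effects: "The model will include dose, study day and dose by study day interaction as fixed categorical effects", with baseline as a continuous covariate.
- Random and residual parts: "Subject will also be included in the model as a random effect. An unstructured covariance matrix will be used to model the within-subject errors".
- Fallback: "If model fitting issues occur with the unstructured covariance matrix", then "other covariance structures including Toeplitz, compound symmetry, and autoregressive (1) will be considered".
- Choice among structures: "the competing models will be ranked according to their AIC, with the one having the lowest AIC being the best".
- Degrees of freedom: "The Kenward-Roger approximation will be used to estimate denominator degrees of freedom".

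SAP 6.2.3 reports and plots the model-based mean and two-sided 80% interval by dose and study day. The SAP nowhere says that the random effect is dropped when the residual matrix is unstructured.

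**The concern.** There are two linked issues.

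First, the text asks for a random subject effect and, separately, a fully free within-subject covariance. Read in the usual way, as a random intercept, the first term adds the same constant to every element of a matrix whose elements are all already free. Software may then report a singular Hessian or set the intercept variance to zero. Kenward-Roger uses the covariance matrix of the variance-parameter estimates, and AIC needs a parameter count. Both are ill-defined when one parameter is redundant. The resulting warning could also be taken as the fitting problem that permits leaving the unstructured model.

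Second, Toeplitz, compound symmetry and AR(1), in the forms named, all impose one variance on every visit. Toeplitz and AR(1) also index visits by order and not by elapsed time. The documents give some reason to doubt equal variance. Protocol 1.3.1.3 describes PD response as generally exposure-dependent, and Table 3 shows wide between-subject variation in exposure (300 mg SC: geometric CV 63% for Cmax, 68% for AUClast). By Day 113, SC subjects are 113 − 78 = 35 days past their last dose and IV subjects 113 − 57 = 56 days. Spread off drug may therefore differ from spread on drug. If it does, the intervals by dose and day are miscalibrated.

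**Working it through.** The plan states no precision or power for the PD model, so there is no figure of that kind to reproduce.

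**Inputs.** The Schedule of Activities gives PD sampling after baseline on Days 2, 4, 8, 15, 22, 29, 30, 33, 57, 85 and 113, so T = 11. Protocol Table 6 agrees for SC cohorts: 11 study-period samples + 1 follow-up = 12, less the Day 1 pre-dose baseline = 11. Protocol Table 7 has one more for the IV cohort (12 + 1 − 1 = 12), the Day 1 post-infusion sample. About 24 subjects are planned in 4 cohorts of 6.

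**Step 1: parameter count.** The marginal covariance is V = σ_b²·J + R, with J the all-ones matrix. Unstructured R has T(T+1)/2 = 11 × 12/2 = 66 parameters, and σ_b² makes 67. The derivative of V with respect to σ_b² is J, which is already a sum of the unstructured basis matrices, so the rank stays at 66. The same check for each structure with the random effect kept (T = 11):

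| R | Parameters with random effect | Rank |
|---|---|---|
| Unstructured | 67 | 66 |
| Toeplitz | 12 | 11 |
| Compound symmetry | 3 | 2 |
| AR(1) | 3 | 3 |

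With T = 12, unstructured gives 79 parameters and rank 78. The redundancy also affects two of the three named fallbacks, but not AR(1).

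**Step 2: effect on the fit.** In a simulated data set of the planned size (24 subjects, 4 cohorts, 11 visits, 4 × 11 + 1 = 45 fixed effects), V was held fixed, σ_b² was set to 0, 0.25, 0.50, 0.75 and 0.95, and R was taken as V − σ_b²·J. R stayed positive definite each time (smallest eigenvalue 0.3587 falling to 0.3564), and −2 REML log-likelihood was 379.72943877 in all five cases. The likelihood is flat in that direction. Fixed-effect estimates depend only on V, so they do not move.

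**Step 3: is unstructured feasible without the random effect?** There are at most 24 × 11 = 264 observations for 66 covariance parameters. With complete data, 24 − 4 − 1 = 19 subject-level degrees of freedom remain against 11 visits. The model is estimable but demanding, so a fallback is plausible in any case.

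**Step 4: named fallbacks.** All three have a constant diagonal, and a random intercept keeps it constant. The gaps between successive sampling days run from 1 day (Day 29 to 30) to 28 days (Day 57 to 85, and Day 85 to 113). Toeplitz and AR(1) treat these as the same lag.

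**Step 5: what a common variance could do to an 80% interval.** Large-sample coverage at visit j is 2Φ(1.2816 × s̄/s_j) − 1, where s̄² is the mean of the visit variances. Both the SD ratio and the pattern across visits are assumptions. Example with 3 visits at SD 1 and 8 at SD 2: s̄² = (3 × 1 + 8 × 4)/11 = 3.18 and s̄ = 1.784. The low-variance z is 1.2816 × 1.784 = 2.286, giving 97.8%. The high-variance z is 2.286/2 = 1.143, giving 74.7%.

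| Assumed pattern | SD ratio | Low-variance visit | High-variance visit |
|---|---|---|---|
| Linear rise over 11 visits | 1.5 | 89% | 72% |
| Linear rise over 11 visits | 2 | 95% | 67% |
| Linear rise over 11 visits | 3 | 99% | 63% |
| 3 low, 8 high | 2 | 97.8% | 74.7% |
| 3 low, 8 high | 3 | 99.9% | 73.5% |

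**Step 6: after the change.** Without the random effect, unstructured (66 parameters, rank 66), Toeplitz (11, 11) and compound symmetry (2, 2) are identifiable. So are heterogeneous Toeplitz (21, 21), heterogeneous compound symmetry (12, 12) and heterogeneous AR(1) (12, 12).

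**The case against.** The best defence is that the redundancy is harmless in practice. The estimates depend only on the marginal covariance. If the software sets the intercept variance to zero, the fit is plain unstructured, which is what one would want, and an experienced statistician would drop the term before abandoning unstructured. This stands as far as the means are concerned. It leaves the Kenward-Roger calculation, the AIC count and the undefined trigger unresolved on paper.

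The fallback list is also open-ended, so heterogeneous structures are not forbidden. That is correct. The point is only that none is named in advance.

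The model-based intervals are not the only PD output either. SAP 6.2.3 also gives visit-specific SDs, geometric CVs, ranges and individual plots, and a separate Emax model, so unequal variance would be visible. The possible pooling of ABR across doses if the PD effect plateaus (SAP 6.2.1.2) does not mention interval width. This stands and limits the consequence.

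Finally, removing the subject effect everywhere would go too far. With AR(1) it is identifiable, and it lets correlation fall to a floor and not to zero, which eases the uneven-spacing problem. This stands, and the recommendation is limited accordingly.

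**Conclusion.** The point holds as a specification defect of low severity. The random effect is redundant under unstructured, Toeplitz and compound symmetry, assuming it is a random intercept, and the named fallbacks all assume equal variance across visits.

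A reader might infer three stronger things that the documents do not support:

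- That the PD estimates would be biased. They would not, because the likelihood and the marginal covariance are unchanged.
- That the redundancy will cause the move to the fallbacks. It may, but unstructured alone is demanding with about 24 subjects, so the cause could not be attributed to the random effect.
- That the coverage figures describe this trial. They do not. No PD variance by visit is given, and the range of about 95% to 99.9% at low-variance visits and 63% to 75% at high-variance visits rests on assumed SD ratios of 2 to 3, two assumed patterns, a large-sample formula and a fitted variance equal to the simple mean. With equal variances, coverage is the nominal 80%.

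PD is a secondary endpoint with no formal test, so the effect is confined to the model-based intervals.

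**What to change.** In SAP 5.2.4:

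- Remove the random subject effect when the residual covariance is unstructured, Toeplitz or compound symmetry. It may stay with AR(1) or with a spatial power structure on actual study days.
- Keep unstructured as the first choice. Add to the named fallbacks heterogeneous Toeplitz, heterogeneous compound symmetry, and either heterogeneous AR(1) or spatial power on actual days. Spatial power with a single variance addresses the spacing only, so visit-specific variances are needed if it is to address both problems.
- Keep the lowest-AIC rule, applied among models that converge, and keep Kenward-Roger.

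The cost is a few sentences and no new data. A heterogeneous fallback carries 10 more variance parameters than its equal-variance counterpart (Toeplitz 11 to 21, compound symmetry 2 to 12, AR(1) 2 to 12), which is not trivial with about 24 subjects. AIC charges 2 × 10 = 20 units for them, so the simpler structure is still chosen when the data do not support unequal variances.

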5.3. Methods to Manage Missing Data

5.3.1. Safety Endpoints

For the analysis of safety endpoints, the sponsor data standard rules for imputation will be applied.

5.3.2. PK Endpoints

5.3.2.1. Concentrations Below the Limit of Quantification

In all data presentations (except listings), concentrations below the limit of quantification (BLQ) will be set to zero. (In listings BLQ values will be reported as "<LLQ", where LLQ will be replaced with the value for the lower limit of quantification.) For PK calculations, BLQ will be handled by the Pfizer standard processes. For PD calculations, BLQ values will be imputed as 0.5*LOQ in calculations.

5.3.2.2. Deviations, Missing Concentrations and Anomalous Values

In summary tables and plots of median profiles, statistics will be calculated having set concentrations to missing if one of the following cases is true:

1. A concentration has been collected as ND (ie not done) or NS (ie no sample),
2. A deviation in sampling time is of sufficient concern or a concentration has been flagged anomalous by the pharmacokineticist.

Note that summary statistics will not be presented at a particular time point if more than 50% of the data are missing.

5.3.2.3. Pharmacokinetic Parameters

Actual PK sampling times will be used in the derivation of PK parameters.

If a PK parameter cannot be derived from a subject's concentration data, the parameter will be coded as NC (ie not calculated). (Note that NC values will not be generated beyond the day that a subject discontinues.)

In summary tables, statistics will be calculated by setting NC values to missing; and statistics will be presented for a particular dose with $\geq 50\%$ evaluable measurements.

If an individual subject has a known biased estimate of a PK parameter, this will be footnoted in summary tables and will not be included in the calculation of summary statistics or statistical analyses.

